Funding: No funding to report as of now. Funding by The Research Council of Norway is proposed after evaluation the developed prototype mentioned in this article.

Correspondence concerning this article should be addressed to [name]

IIIT Delhi University, [name].

Email: [contact]

ABSTRACT

Background: To take the existing VR technology to the next level, we developed a novel Intelligent Virtual Reality Therapy System (IVRTS). Aim: The objective of this project had three aspects: Namely, development of the novel IVRTS technology involving the development of a hardware device, development of Artificially Intelligent Psychotherapeutic software-interface and testing it's clinical efficacy. *Methods*: It used a two-phased methodology; Development of the novel technology and testing its Clinical Efficacy. After development of Novel IVRTS. A 7-week intervention was designed for each subject. The sample of 500 patients, meeting the criteria of Acrophobia and Anxiety, underwent the interventions at The GTB hospital (The University of Delhi), for a total 3500 sessions, ranging 5250 hours for over 2 years. The subjects were randomly divided into 4 groups: IVRTS Group, Mindfulness group, CBT group and Control Group. *Registration:* The ethics committee and clinical trial registration number is 3/1/333011/HRD. *Results*: The IVRTS group reported significant reduction in Acrophobic and Anxiety symptoms. The Pre and Post intervention, mean and SD reduced from 28.60±8.45 to 11.10±4.03 on HAMA; from 8.10±1.56 to 3.73±1.23 on SUDS and increased from 72.87±6.21 to 87.07±3.79 on WHO-QOL-BREF. It was also seen the mean comparison of reduction was significantly higher compared to the CBT and Mindfulness Groups. It also indicated enhanced Quality of Life (p < .001) compared to The Mindfulness Group and CBT Group. *Conclusion:* IVRTS decreased symptoms of Acrophobia and Anxiety, enhanced Quality of Life significantly than other treatment groups. Development of this technology is a land-mark innovation.

Key Words: Anxiety; Virtual Reality; Phobias; Treatment Intervention.

INTRODUCTION

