(CBT) states that it is not the situation itself but the thought associated with the situation (stimulus) which makes an individual fearful. Altering this thought and the emotions related to it is hence helpful in treating phobias. This was achieved by integrating an automated intelligent Cognitive Behavior Therapy software program with the VR device. 4) Finally, the researchers used Mindfulness Relaxation as a treatment for phobia. This was implemented by making the subject face the anxiety-provoking situation with the help of VR equipment and simultaneously working on reducing the anxiety emotions with the help of guided mindfulness meditation accompanied by meditation music, along with the developed automated intelligent therapy software interface. This methodology was intended to put the subject in a peaceful state of mind, detaching them from negative thoughts and fears, working on the principle that anxiety and relaxation cannot coexist.

[figure not shown]

Figure 6: Understanding CBT Software

Project Plan

[figure not shown]

Figure 7: Project plan

01/08/2020

OUTCOMES AND RESULTS

The quantitative and qualitative results were analyzed with the appropriate statistical and analytical tools. Various statistical modalities were used to establish efficacy, efficiency and the frequencies evaluated. Paired sample t- test were conducted in this study to assess the statistical significance of the interventions.

Independent sample t-test and ANOVA were tested in the data. Correlation analysis was also performed, The association between two categorical variables is enumerated by Chi-square test.

Scale	Mindfulness (n=118)		Control (n=125)		t-	F-	p-value
	Pre	Post	Pre	Post	value	value	
	Mean±SD		Mean±SD				
HAMA	32.86±5.76	19.62±4.24	33.70±6.08	28.00±6.49	8.350	2.327	0.000
SUDS	8.24±0.95	5.69±1.04	8.27±1.11	6.03±1.29	1.228	0.178	0.225
QOL	73.86±7.73	84.10±5.19	75.47±5.44	82.53±4.85	-2.229	6.242	0.030

Table 1: Mean comparison between Mindfulness Meditation group (n=118) and control group (n=125)

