Table 1 represents the mean comparison between Mindfulness group and the Control Group of respondents while before and after intervention. On The Hamilton Anxiety scale, most of the respondents in The Mindfulness Group had very severe condition while before intervention with mean score (M=32.86), but it reduced to mean score (M=19.62). While in the control group, most of the respondents had very severe condition while before intervention with mean score (M=33.70) and moderate to severe condition while after intervention with mean score (M=28.00). The obtained t-value and p-value for Hamilton scale are 8.350 and 0.000 respectively. Here, p-value is less than 0.01; it indicates that there is a statistically significant difference between mindfulness and control group of respondents based on Hamilton scale. Similarly when considered the Subjective Unites of Dysfunction Scale (SUDS), most of the respondents of The Mindfulness Group, felt 'Freaking out' while before intervention with mean score (M=8.24) and 'Moderately upset' while after

intervention with mean score (M=5.69). But in the control group, most of the respondents felt 'Freaking out' while before intervention with mean score (M=8.27) and 'bad' while after intervention with mean score (M=6.03). The obtained t-value and p-value for SUDS are 1.228 and 0.225 respectively. Here, p-value is greater than 0.05, and indicated that there is no significant difference between mindfulness and control group of respondents based on SUDS. Similarly, obtained t-value and p-value for Quality of life are -2.229 and 0.030. Here p-value is less than 0.05; and shows a statistically significant difference between Mindfulness and Control group in relation to WHO Quality of life (QOL - BREF) scale of respondents.

	CBT (n=106)		Control (n=125)				
Scale	Pre	Post	Pre	Post	t-	F-	p-
	Mean±SD		Mean±SD		value	value	value
HAMA	32.52±5.24	21.03±4.29	33.70±6.08	28.00±6.49	6.905	2.312	0.000
SUDS	8.24±0.98	5.34±1.14	8.27±1.11	6.03±1.29	2.366	0.344	0.021
QOL	73.62±5.23	83.28±5.06	75.47±5.44	82.53±4.85	-2.714	0.002	0.009

Table 1: Mean comparison between CBT group (n=106) and Control group (n=125)

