Table 2 presents the mean comparison between CBT group and control group of respondents before and after intervention. On the Hamilton Anxiety scale, most of the respondents of the CBT Group had very severe condition while before intervention with mean score (M=32.52), which reduced to mild to moderate severe after the intervention witj mean score (M=21.03). In control group, most of the respondents were in very severe condition while before intervention with mean score (M=33.70) and improved to moderate to severe condition after the intervention with mean (M=28.00). The obtained t-value and p-value for Hamilton scale are 6.905 and 0.000 respectively. Here, p-value is less than 0.01, it indicates a statistically significant difference between CBT and control group of respondents based on Hamilton Anxiety scale. Similarly, on the SUDS of respondents, most of the respondents felt 'Freaking out' while before intervention with mean (M=8.24) and

'Moderately upset' after the intervention with mean (M=5.34). But in the control group, most of the respondents felt 'Freaking out' before the intervention with mean (M=8.27) and felt 'bad' after intervention with mean (M=6.03). The obtained t-value and p-value for SUDS is 2.366 and 0.021 respectively. Here, p-value is less than 0.05, indicating a statistically significant difference between CBT and control group of respondents based on SUDS. Similarly obtained t-value and p-value for Quality of life are -2.714 and 0.009. Here p-value is less than 0.01; indicating a statistically significant difference between CBT and Control group in relation to The WHO Quality of life (QOL- BREF) scale of respondents.

	Novel IVRTS (n=115)		Control (n=125)		t-	F-	
Scale	Pre	Post	Pre	Post	_		p- value
	Mean±SD		Mean±SD		value	value	value
HAMA	28.60±8.45	11.10±4.03	33.70 ± 6.08	28.00±6.49	8.088	23.503	0.000
SUDS	8.10±1.56	3.73 ± 1.23	8.27±1.11	6.03 ± 1.29	7.503	2.315	0.000
QOL	72.87±6.21	87.07±3.79	75.47±5.44	82.53±4.85	-6.313	4.519	0.000

Table 3: Mean comparison between IVRTS (n=115) and Control group (n=125)

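### QOL comparisons with Control ignore a higher Control baseline and never state whether post or change scores were tested; the CBT result is the most sensitive to that choice

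*Combined protocol and SAP*

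**What the plan says.** Under OUTCOMES AND RESULTS the between-group methods are given in one sentence: "Independent sample t-test and ANOVA were tested in the data". Paired t-tests are also named. No baseline covariate is mentioned.

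QOL means and SDs before and after treatment appear in three pairwise tables: "Mean comparison between Mindfulness Meditation group (n=118) and control group (n=125"), "Mean comparison between CBT group (n=106) and Control group (n=125") and "Mean comparison between IVRTS (n=115) and Control group (n=125"). The CBT table is captioned Table 1 a second time, but the text calls it Table 2. Each table gives one t-value and one p-value per scale, without saying which score the t-value compares.

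For CBT the "obtained t-value and p-value for Quality of life are -2.714 and 0.009", which the text interprets as "indicating a statistically significant difference between CBT and Control group in relation to The WHO Quality of life". The Abstract speaks of comparing mean reductions, and gives the IVRTS QOL course as "72.87±6.21 to 87.07±3.79 on WHO-QOL-BREF". The text on Table 4 instead compares means after intervention.

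**The concern.** Control starts with the highest mean QOL. An unadjusted comparison then depends on the score used. A test of post scores gives the treated arms no credit for starting lower. A test of change scores credits them with the whole gap, although part of it would be expected to close through regression to the mean. ANCOVA lies between the two and removes the choice.

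At stake are the QOL claims for CBT and Mindfulness against Control, and the size of the IVRTS effect behind the Control part of hypothesis (iii). The CBT claim is the most exposed, because its post-score difference is small and most of its change difference is the baseline gap.

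**Working it through.** **Inputs** (QOL rows of the three pairwise tables, mean±SD; change by subtraction):

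| Arm | n | Pre | Post | Change |
|---|---|---|---|---|
| Control | 125 | 75.47±5.44 | 82.53±4.85 | 7.06 |
| Mindfulness | 118 | 73.86±7.73 | 84.10±5.19 | 10.24 |
| CBT | 106 | 73.62±5.23 | 83.28±5.06 | 9.66 |
| IVRTS | 115 | 72.87±6.21 | 87.07±3.79 | 14.20 |

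Printed QOL |t|: 2.229 (Mindfulness), 2.714 (CBT), 6.313 (IVRTS). The pre-post correlation r is not given.

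**1. Reproducing the CBT figure from post scores.** Pooled SD = √[(105×5.06² + 124×4.85²)/229] = 4.947. SE = 4.947×√(1/106 + 1/125) = 0.653. t = 0.75/0.653 = 1.15, p=0.25. The printed 2.714 would need SE = 0.75/2.714 = 0.276. At this SD that takes 2×(4.947/0.276)², or about 640 per arm, more than the whole trial of 500. A smaller n makes it worse: at 30 per arm the SE is 1.28. The figure is not reproduced.

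**2. Degrees of freedom.** On 106+125−2 = 229 df, t=2.714 gives p=0.0072, not 0.009. A p that rounds to 0.009 (0.0085 to 0.0095) needs about 65 down to 43 df. For Mindfulness, t=2.229 on 241 df gives p=0.0267; the printed 0.030 needs about 48 to 61 df. Both suggest roughly 30 per arm.

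**3. Differences from Control at the stated n:**

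| Arm | Baseline gap (p) | Post difference (t; p) | Change difference | Gap as share of change |
|---|---|---|---|---|
| Mindfulness | −1.61 (0.06) | 1.57 (2.44; 0.016) | 3.18 | 51% |
| CBT | −1.85 (0.009) | 0.75 (1.15; 0.25) | 2.60 | 71% |
| IVRTS | −2.60 (0.0006) | 4.54 (8.03; <0.001) | 7.14 | 36% |

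**4. Do change scores fit the printed t-values?** The SD of change in an arm is √(SDpre² + SDpost² − 2r·SDpre·SDpost). Solving for the r that reproduces each printed t:

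- At the stated n: r = −0.82 (Mindfulness), 0.01 (CBT), −0.47 (IVRTS). These are implausible for repeated QOL scores.
- At 29 treated and 30 Control (57 df, an assumption): r = 0.60, 0.75, 0.68. These are plausible. For CBT the pooled SD of change is 3.68, SE = 3.68×√(1/29 + 1/30) = 0.958, t = 2.60/0.958 = 2.71, p=0.009.

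**5. ANCOVA in that scenario.** Adjusted difference = post difference − b×baseline gap, where b is the pooled within-arm slope at the r above.

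| Arm | b | Adjusted difference | Change ÷ adjusted | ANCOVA p |
|---|---|---|---|---|
| Mindfulness | 0.446 | 1.57 + 0.446×1.61 = 2.29 | 3.18/2.29 = 1.39 | 0.037 |
| CBT | 0.693 | 0.75 + 0.693×1.85 = 2.03 | 2.60/2.03 = 1.28 | 0.024 |
| IVRTS | 0.502 | 4.54 + 0.502×2.60 = 5.85 | 7.14/5.85 = 1.22 | <0.001 |

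**6. CBT ANCOVA if the stated n is right (106/125), by assumed r:** r=0: 0.75, p=0.26; r=0.3: 1.26, p=0.048; r=0.5: 1.61, p=0.006; r=0.7: 1.95, p=0.0001. The result is below 0.05 once r is about 0.29 or more, and below 0.01 once r is about 0.46 or more.

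**7. IVRTS versus Control.** The post-score test at 30 per arm gives t=4.04, p=0.0002. Every other analysis run, at either n, gives p<0.001.

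**The case against.** A reader might infer that the QOL effects are overstated. The documents do not support that as a flat statement, because the score tested is never given. For post scores, which the text on Table 4 argues from, the higher Control baseline works against the treated arms: with a positive pre-post correlation, each ANCOVA estimate exceeds the post difference. The overstated direction needs change scores, and these fit the printed t-values plausibly only at about 30 per arm.

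A reader might also infer that the CBT claim depends on the imbalance. This is not shown. At the correlation that reproduces the printed CBT t, ANCOVA still gives about 2.0 with p of about 0.02. At the stated n it is below 0.05 for any r of about 0.29 or more. Larger overstatement can be produced by assuming r=0.3, but in the 30-per-arm scenario that value contradicts the printed t.

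Nor is the imbalance clearly more than chance. At the stated n the IVRTS gap has p=0.0006. At 30 per arm, where the change-score reading fits, the three gaps have p of about 0.09 (IVRTS), 0.18 (CBT) and 0.35 (Mindfulness). The treated-arm baselines may also describe only those analysed (106, 118 and 115 of 125 assigned), which the documents do not clarify.

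These objections stand, and they narrow the point. They do not remove it: adjustment is absent, the score and the effective n are unclear, and the CBT figure cannot be reproduced from post scores.

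**Conclusion.** The point holds in limited form, with moderate confidence. Control has the highest baseline QOL, the named between-group tests do not adjust for it, and the score tested is undocumented. The choice matters most for CBT versus Control: 0.75 (p=0.25) on post scores at the stated n, against 2.60 on change scores. The printed t=-2.714 with p=0.009 is compatible neither with the printed post scores nor with 229 df.

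Under the assumption of change scores at about 30 per arm, unadjusted differences exceed ANCOVA by about 39% (Mindfulness), 28% (CBT) and 22% (IVRTS), and CBT moves from p=0.009 to about p=0.02: weaker, but not overturned. These sizes rest on correlations inferred from the printed t-values, not reported ones. If post scores were tested, the direction reverses.

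It would be wrong to conclude that IVRTS superiority over Control on QOL is in doubt. It is significant under every analysis tried; only its size changes.

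**What to change.** State in Tables 1 to 3 which score was tested and how many patients entered each test, and reconcile both with the printed t and p values. This comes first, because the adjusted p-values cannot be interpreted until n is settled.

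Then replace the independent t-tests for QOL, HAM-A and SUDS by ANCOVA of the post score on arm with the pre score as covariate. Report adjusted differences with 95% CIs, and restate the CBT and Mindfulness QOL claims from those results.

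The cost is re-analysis only, since the baseline scores are already collected; this is a free improvement. QOL effects may look less favourable than change scores suggest. For IVRTS on HAM-A the adjustment goes the other way. IVRTS started 5.10 points lower (28.60 against 33.70), so its reduction exceeds Control's by 17.50 − 5.70 = 11.80, while the post difference is 16.90. With a slope between 0 and 1, ANCOVA falls between these and so above the change difference.

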Figure 2: Intelligent Interactive Psychotherapy Program Software (IIPPS)

Objective

To develop Novel Technology, Intelligent Virtual Reality Therapy System (IVRTS) and test its Clinical Efficacy to treat phobias and anxiety, compared to Mindfulness Meditation and Cognitive Behavior Therapy (Talk Therapy).

Concept

Virtual Reality has a vast potential in healthcare. One such area where VR is becoming a promising technique is the treatment of Phobias and Anxiety Disorders. There are various types of phobias, and amongst them, some occur more commonly in individuals, in general. In the treatment of phobia using VR, the patient re-enters a computer-generated environment that is the imitation of the situation or an object the patient possesses the fear of. It helps people to encounter situations or objects they fear while being in a completely safe and controlled environment. The environment is

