In this health-related research, the researchers first applied to health research ethics committees for permissions and once the permissions are taken, then the researchers identified the sample or user groups, through seminars at the Gjøvik hospital, using social media, etc. The researchers made sure that the user consent is received, the participation in our studies are voluntary and their participation can be ended any time by the user without any penalties for the user. Also, the Clinical Trials took place at The Psychiatry OPD of the Guru Tegh Bahadur Hospital of The University of Delhi.

Figure 4: The software detects the pupil, after detection it determines the focus point of gaze to control the virtual interaction

Hypothesis:

- (i) The new novel developed technology Intelligent Virtual Reality Therapy System (IVRTS) is more effective in reducing symptoms of Phobia and Anxiety as compared to Mindfulness Meditation and Cognitive Behavior Therapy Groups.
- (ii) The novel IVRTS Group scores significantly lower on both Hamilton Anxiety Inventory (HAM-A) and Subjective Units of Dysfunction Scale (SUDS) compared to all three, The Control Group, The Mindfulness Group Cognitive Behavior Therapy (CBT) Group.
- (iii) The Novel IVRTS Group scores significantly higher on WHO Quality of Life Scale (WHO QOL BREF) compared to all three, The Control Group, The Mindfulness Meditation Group and The CBT Group.
- (iv) The new technology proves to be effective and a steppingstone towards a newer era in the treatment of Mental Health issues using Mental healthcare engineering.

Sample

The Clinical Trials were carried out on 500 adults with Acrophobia which is fear of heights co-morbid with Generalized Anxiety. The sample for the study was recruited from the patients/subjects attending the adult psychiatric OPD of the department of Psychiatry GTB Hospital of The University of Delhi and fulfilling the

ICD-10 diagnostic criteria for assessment of Acrophobia and generalized anxiety. The study was conducted on an initial 500 subjects attending the psychiatric OPD of the department of Psychiatry GTB Hospital of the University of Delhi. The subjects were equally and randomly assigned to three groups namely; Novel Intelligent Virtual Reality System (IVRTS) Group (n=125), Mindfulness Meditation Group (n=125), Cognitive Behavior Therapy (CBT) Group (n=125) and The Control Group (n=125).

[figure not shown]

Figure 5: Consort Diagram

Inclusion Criteria

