Table 3 presents the mean comparison between The Novel Intelligent Virtual Reality Therapy System (IVRTS) and control group of respondents. On the Hamilton Anxiety scale of, most of the respondents of the Novel IVRTS Group had a score representing moderate to severe condition before the intervention with mean (M=28.60), and reduced to mild condition after the intervention with mean (M=11.10). In the control group, most of the respondents were in very severe condition before intervention with mean (M=33.70) and moved to moderate to severe condition after intervention with mean (M=28.00). The obtained t-value and p-value for Hamilton Anxiety scale is 8.088 and 0.000 respectively. Here, p-value is less than 0.01, it indicates that there is a statistically significant difference between The Novel IVRTS Group and The Control Group on Hamilton scale. Similarly, on the SUDS of respondents, most of the respondents of The IVRTS Group felt 'Freaking out' before the intervention (M=8.10) and 'No Significant Distress' after the intervention with mean

(M=3.73). In the control group, most of the respondents felt 'Freaking out' before the intervention with mean (M=8.27) and moved to feeling 'bad' after the intervention with mean with mean (M=6.03). The obtained t-value and p-value for SUDS are 7.503 and 0.000 respectively. Here, p-value is less than 0.01, it indicates that there is a statistically significant difference between The Novel IVRTS Group and The Control group based on SUDS. Similarly, the obtained t-value and p-value for The WHO Quality of life Scale were -6.313 and 0.009. Here p-value is less than 0.01, and indicates a statistically significant difference between The Novel IVRTS and Control group on The WHO Quality of life (QOL-BRF) scale of respondents.

Scale	Mindfulness		CBT		Novel IVRTS		
	Pre	Post	Pre Post		Pre	Post	
	Mean±SD		Mean±SD		Mean±SD		
HAMA	32.86±5.76	19.62±4.24	32.52±5.24	21.03±4.29	28.60±8.45	11.10 ± 4.03	
SUDS	8.24 ± 0.95	5.69 ± 1.04	8.24 ± 0.98	5.34 ± 1.14	8.10 ± 1.56	3.73 ± 1.23	
QOL	73.86±7.73	84.10±5.19	73.62±5.23	83.28±5.06	72.87±6.21	87.07±3.79	

Table 4: Efficacy of Interventions based on the HAMA, SUDS and WHO QOL scale

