Finally Table 4, shows the comparison analysis between the various interventions to show which intervention proved to be the most effective and efficient for the patients. Interventions namely, Mindfulness Meditation, CBT and Novel Intelligent Virtual Reality Therapy System (IVRTS). The mean scores after intervention on both The Hamilton Anxiety Scale and The Subjective Units of Dysfunction Scale for the Novel IVRTS Group is significantly less than the mean scores (HAMA=11.10, SUDS=3.73) of The Mindfulness Group (HAMA=19.62, SUDS=5.69) and the CBT Group (HAMA=21.03, SUDS=5.34). In addition, The Novel IVRTS Group has a higher mean score on The WHO Quality of Life Scale (QOL=87.07) compared to the Mindfulness Group (QOL=84.10) and the CBT Group (QOL=83.28). The p-value is less than 0.01 respectively indicating a significant difference between Novel IVRTS compared to other interventions including CBT, Mindfulness and

Control groups. Considering the all the above comparisons of statistical significance modalities namely, The Mean Scores, Standard Deviations, t-scores and p-scores. The study concludes that, The Novel Intelligent Virtual Reality Therapy System (IVRTS) intervention is the most effective and efficient intervention compared to Mindfulness and even CBT.

Through the various approaches explained henceforth, the researchers aspired to create a more effective, image-based treatment system for phobias, based on the combination of principles of Psychology and Virtual Reality. The treatment methodologies thus aimed to automate the process oftherapy thereby making the process faster and more practical.

Moreover, the new technology is for the first time used to develop human, AI interaction for treatment, using interactive sensors, intelligent automated psychotherapy interface, and VR imagery scenarios.

DISCUSSION AND CONCLUSION

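### The main comparison, IVRTS against CBT and Mindfulness, is declared significant with no reported test result, and its post-score basis ignores a HAM-A baseline gap of about 4 points

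*Combined protocol and SAP*

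**What the plan says.** The Objective section sets out to "test its Clinical Efficacy to treat phobias and anxiety, compared to Mindfulness Meditation and Cognitive Behavior Therapy (Talk Therapy"). Hypothesis (i) states that IVRTS "is more effective in reducing symptoms of Phobia and Anxiety as compared to Mindfulness Meditation and Cognitive Behavior Therapy Groups". Hypothesis (ii) expects lower HAM-A and SUDS scores "compared to all three, The Control Group, The Mindfulness Group Cognitive Behavior Therapy (CBT) Group", and hypothesis (iii) makes the matching claim for quality of life.

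On methods, Outcomes and Results says "Independent sample t-test and ANOVA were tested in the data". It names no baseline adjustment and no multiplicity control.

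The results are laid out as follows:

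- Tables 1 to 3 (the CBT table carries a second Table 1 caption) give t, F and p for Mindfulness, CBT and IVRTS, each against control. The IVRTS table is captioned "Table 3: Mean comparison between IVRTS (n=115) and Control group (n=125").
- "Table 4: Efficacy of Interventions based on the HAMA, SUDS and WHO QOL scale" is the only table with the active arms side by side. It has pre and post means and SDs, and no test column.
- The text on Table 4 argues from "The mean scores after intervention on both The Hamilton Anxiety Scale and The Subjective Units of Dysfunction Scale for the Novel IVRTS Group" and then concludes "The p-value is less than 0.01 respectively indicating a significant difference between Novel IVRTS compared to other interventions", naming CBT, Mindfulness and control together.
- The abstract says that the reduction was significantly greater than with CBT and Mindfulness, and gives p < .001 against both for quality of life only.

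**The concern.** The head-to-head comparison is the trial's main question and its headline conclusion, yet it is the one comparison with no reported test. A single p bound covers three scales and three comparators. The reader cannot tell whether post scores or changes were tested, which test was used, how many patients entered it, or how precise the difference is.

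The choice of quantity matters on HAM-A. IVRTS started in a milder state: the document's own wording puts it at moderate to severe before treatment and the two comparators at very severe. A comparison of post means credits IVRTS with part of a gap that existed before treatment. A claim of superiority over an established therapy rests on this.

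**Working it through.** **Inputs.** Pre and post means and SDs come from Tables 1 to 4. Arm sizes come from the captions of Tables 1 to 3: IVRTS 115, Mindfulness 118, CBT 106, control 125. The pre-post correlation r is not given, so it is assumed and varied.

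**1. Baseline HAM-A.** Welch t = difference / √(s₁²/n₁ + s₂²/n₂).

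- Against Mindfulness: 28.60 − 32.86 = −4.26; SE = √(8.45²/115 + 5.76²/118) = 0.950; t = −4.49, p = 1.2 × 10⁻⁵.
- Against CBT: 28.60 − 32.52 = −3.92; SE = √(8.45²/115 + 5.24²/106) = 0.938; t = −4.18, p = 4.4 × 10⁻⁵.

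Baseline SUDS differs by 0.14 from both arms, and QOL by 0.99 and 0.75 (p between 0.28 and 0.42). The imbalance among the active arms is on HAM-A only.

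**2. Can the asserted p < 0.01 be reproduced?** Welch tests on post scores at the stated n:

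| Outcome | vs Mindfulness: difference, t | vs CBT: difference, t |
|---|---|---|
| HAM-A | −8.52, −15.7 | −9.93, −17.7 |
| SUDS | −1.96, −13.1 | −1.61, −10.1 |
| QOL | 2.97, 5.00 | 3.79, 6.26 |

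The weakest is QOL against Mindfulness, p = 1.2 × 10⁻⁶. At the stated n the bound holds for all six.

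**3. Size of the HAM-A advantage by quantity.** Mean falls are 28.60 − 11.10 = 17.50 (IVRTS), 32.86 − 19.62 = 13.24 (Mindfulness) and 32.52 − 21.03 = 11.49 (CBT). The change advantage is therefore 4.26 and 6.01.

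For a four-arm baseline-adjusted model, the adjusted difference = post difference − b × pre difference, with b = r·Σ(n−1)s_pre·s_post / Σ(n−1)s_pre², and 459 df.

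| Assumed r | b | vs Mindfulness (95% CI) | vs CBT (95% CI) |
|---|---|---|---|
| 0.3 | 0.215 | −8.52 + 0.215 × 4.26 = −7.60 (−8.85 to −6.36) | −9.93 + 0.215 × 3.92 = −9.09 (−10.36 to −7.81) |
| 0.5 | 0.359 | −6.99 | −8.52 |
| 0.8 | 0.574 | −6.07 (−6.92 to −5.23) | −7.68 (−8.54 to −6.82) |

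With a slope from the two compared arms only, the advantage is 7.8 to 6.6 and 9.3 to 8.2. Over all outcomes, the largest p in the four-arm model is 1.4 × 10⁻⁷ (QOL against Mindfulness, r = 0.3), or 1.3 × 10⁻⁶ after multiplying by nine.

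**4. Can the stated n be relied on?** Stated df are 118 + 125 − 2 = 241 and 106 + 125 − 2 = 229. The printed pairs imply far fewer:

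| t / printed p | Comparison with control | Implied df (about) |
|---|---|---|
| 1.228 / 0.225 | Mindfulness, SUDS | 46 to 59 |
| 2.229 / 0.030 | Mindfulness, QOL | 48 to 62 |
| 2.366 / 0.021 | CBT, SUDS | 55 to 78 |
| 2.714 / 0.009 | CBT, QOL | 43 to 65 |

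Table 3 prints t of 8.088, 7.503 and 6.313 in absolute value (HAM-A, SUDS, QOL). At 115 and 125 patients, post scores give 24.4, 14.1 and 8.1. Change scores, with SD √(s_pre² + s_post² − 2r·s_pre·s_post), give at least 9.99, 8.88 and 7.59 for r ≥ 0. At 30 per arm, change scores match the printed values with r of 0.70, 0.66 and 0.68. This is an inference, not proof.

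**5. If the tests did use about 30 IVRTS and 29 comparator patients (assumption).** On post scores, QOL gives p = 0.016 against Mindfulness and 0.002 against CBT, while HAM-A and SUDS stay below 0.00001. On change scores against Mindfulness:

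| r | HAM-A p | QOL p |
|---|---|---|
| 0 | 0.054 | 0.075 |
| 0.5 | 0.012 | 0.017 |
| 0.7 | 0.003 | 0.004 |

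**The case against.** The strongest reply is that the assertion is true on the document's own figures. A p bound is printed, arm sizes appear beside the same means in Tables 1 to 3, unadjusted differences can be read off Table 4, and all six contrasts are far below 0.01 at those sizes. It can also be said that baseline may not have been ignored. The text never says what the p-value tested, the abstract speaks of reduction, and the Table 3 statistics fit change scores, which already subtract baseline.

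Part of this stands. Significance and direction are not overturned at the stated n. The baseline problem is confined to HAM-A, and adjustment removes only part of the 4-point gap. On QOL, adjustment increases the IVRTS advantage: from 2.97 to between 3.19 and 3.56 against Mindfulness, and from 3.79 to between 3.96 and 4.24 against CBT (r from 0.3 to 0.8).

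It does not answer the point. The comparison in the Table 4 text is argued from post means, and if something else was tested, that is not stated. The printed t and p pairs conflict with the very arm sizes on which the defence depends. At about 30 per arm, the blanket p < 0.01 and the abstract's QOL p < .001 would both fail on post scores.

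**Conclusion.** The concern holds and must be fixed. No estimate, interval, test statistic, df or analysed n is reported for IVRTS against CBT or Mindfulness, and the post-score argument overstates the HAM-A advantage by about 0.8 to 2.4 points relative to a baseline-adjusted estimate. That range assumes a pre-post correlation of 0.3 to 0.8 and a common slope across arms.

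Superiority is not shown to be false. At the stated n every contrast stays significant after adjustment and a nine-fold correction. Whether that reassurance applies depends on the number actually analysed, which the document's own statistics put in doubt; the figure of about 30 per arm remains an inference.

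**What to change.** For each outcome, fit one four-arm linear model of post score on arm and baseline score. Report IVRTS against CBT, Mindfulness and control (hypotheses (ii) and (iii) name all three) with adjusted difference, 95% CI, df, multiplicity-adjusted p (for example Holm over the nine contrasts) and analysed n per arm. State that this analysis was specified after the results were known.

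Add these results to Table 4. Use them to replace the p < 0.01 sentence in the Table 4 text and the abstract's statements on reduction and on QOL.

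Three checks belong with the refit:

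- Reconcile the t and p values in Tables 1 to 3 with the stated arm sizes.
- Account for the 125 patients allocated per arm against the 115, 106 and 118 tabulated, and for a HAM-A imbalance this large after random assignment. Adjustment cannot repair a fault in allocation.
- Check the common slope. With equal r, the within-arm HAM-A slope would be (4.03/8.45)r = 0.48r for IVRTS and (6.49/6.08)r = 1.07r for control.

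The model and text need a few lines of code and no new data; the reconciliation takes longer if the analysed dataset is not settled. The HAM-A advantage will be smaller and adjusted p-values slightly larger, but at the stated n no contrast would lose significance.
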